10.2.2.2 Overview of Adverse Events Rates per 100 Patient-Years of Study Drug Exposure

For each treatment group, the TEAE rate per 100 patient-years of exposure will be calculated overall, for each SOC and each PT, for each of the following events:

- All TEAEs
- Treatment-emergent serious adverse events (SAEs)
- Treatment-emergent severe adverse events
- TEAEs reasonably possibly related to study drug
- TEAEs leading to discontinuation of study drug
- TEAE leading to death

For this calculation, one year will be considered to be 365.25 days. For each treatment group, the numerator of the overall rate, the SOC rate, or the PT rate, will be the total number of TEAEs reported overall, for the SOC, or for the PT, respectively; that is a subject can be counted more than once overall, for a SOC, and for a PT. For each treatment group, the denominator of the rates will be the total number of days exposed to study drug summed across all treated subjects divided by 365.25. The TEAE rate per 100 patient-years of exposure will be calculated as $[(\text{numerator}/\text{denominator})]*100$. The

number of TEAEs reported (numerator), the total number of years of study drug exposure (denominator), and the TEAE rate per 100 patient-years will be presented overall, for each SOC, and for each PT for each treatment group.

As a sensitivity analysis, the AE summary per 100 patient-years of study exposure by SOC and PT will be repeated by exposure groups. In this summary, all AEs with an onset date after the first dose of study drug will be included, regardless of whether the AE occurred more than 30 days after the last dose of study drug. This sensitivity analysis will only be performed in final CSR.

10.2.2.3 Adverse Events of Special Interest Rates per 100 Patient-Years of Study Drug Exposure

The Adverse Events of Special Interest (AESI) categories will be summarized and presented for each treatment group and overall using SOC and MedDRA PT (for adjudicated cardiovascular events, the CAC adjudicated categories will be used). The AESI categories will be identified per Standard MedDRA Queries (SMQs)/Company MedDRA Queries (CMQs).

For each treatment group, the treatment-emergent Adverse Events of Special Interest (AESI) rate per 100 patient-years of exposure will be calculated overall, for each SOC and each PT, for each of the AESI listed in Section [10.2.1.6](#).

For this calculation, one year will be considered to be 365.25 days. For each treatment group, the numerator of the overall rate, the SOC rate, or the PT rate, will be the total number of TEAEs reported overall, for the SOC, or for the PT, respectively; that is a subject can be counted more than once overall, for a SOC, and for a PT.

For each treatment group, the denominator of the rates will be the total number of days exposed to study drug summed across all treated subjects divided by 365.25. Please refer to Section [8.1](#) for the calculation of study drug exposure. The TEAE rate per 100 patient-years of exposure will be calculated as $[(\text{numerator}/\text{denominator})]*100$. The number of TEAEs reported (numerator), the total number of years of study drug exposure

(denominator), and the TEAE rate per 100 patient-years will be presented overall, for each SOC, and for each PT for each treatment group.

10.2.2.4 Listing of Serious Adverse Events (Including Deaths) and Adverse Events Leading to Study Drug Discontinuation

All serious adverse events (SAEs), deaths, and adverse events leading to discontinuation of study drug will be listed.

10.3 Analysis of Laboratory Data

10.3.1 Variables and Units

All laboratory parameters to be collected in this study are listed below. Laboratory parameters will be reported using the standard international (SI) units.

Table 13. List of Laboratory Variables

Laboratory Variables
Hematology
White Blood Cell (WBC) Count
Red Blood Cell (RBC) Count
Hemoglobin
Hematocrit
Platelets count
Neutrophils
Basophils
Eosinophils
Lymphocytes
Monocytes
Bands
Chemistry
Total Bilirubin
Alkaline Phosphatase (ALP)
Serum glutamic oxaloacetic transaminase (SGOT/AST)
Serum glutamic pyruvic transaminase (SGPT/ALT)

Table 13. List of Laboratory Variables (Continued)

Laboratory Variables
Chemistry (continued)
Total Protein
Albumin
Glucose
Triglycerides
Blood Urea Nitrogen (BUN)
Creatinine
Uric acid
Sodium
Potassium
Calcium
Inorganic Phosphorus
Creatine Phosphokinase (CPK)
Chloride
Bicarbonate
Cholesterol
LDL cholesterol
HDL cholesterol
LDL/HDL ratio
Cholesterol/HDL ratio
International Normalized Ratio (INR) reflux only
Urinalysis
Specific Gravity
pH
Protein
Glucose
Ketones
Blood
Microscopic Examination (if needed)
Urobilinogen
Bilirubin
Leukocytes

Table 13. List of Laboratory Variables (Continued)

Laboratory Variables
Urinalysis (continued)
Nitrites
Other
hs-CRP
QuantiFERON-TB Gold
IgG and IgM
ESR

10.3.2 Analysis of Laboratory Data Prior to Protocol-Defined Treatment Switching at Week 26

10.3.2.1 Assessment of Mean Change from Baseline in Clinical Laboratory Variables

Analyses of mean change from baseline in continuous hematology, chemistry, and urinalysis variables which are measured longitudinally will be performed by visits and by "as treated" treatment group. For each change from baseline analysis, the following summary statistics will be presented for each treatment group: sample size, baseline mean, visit mean, and the mean, standard deviation, and median of the changes from baseline.

In addition, similar analyses will be conducted for percentage change from baseline in hemoglobin, LDL-C, HDL-C, triglycerides, total cholesterol (TC), TC/HDL and LDL/HDL.

Plot for each treatment group over time will be provided for key lab parameters.

10.3.2.2 Assessment of Shift from Baseline in Clinical Laboratory Variables

The baseline and post-baseline laboratory observations will be categorized as Grade 1, Grade 2, Grade 3, and Grade 4 according to OMERACT criteria (Rheumatology Common

Toxicity Criteria v.2.0). For creatine phosphokinase and creatinine, NCI CTC criteria will be used.

For each laboratory variable, shift tables will be generated that cross-tabulate the subjects as deemed appropriate by "as treated" treatment group:

- Category of the baseline value versus category of the final value,
- Category of the baseline value versus maximum category.
- Category of the baseline value versus minimum category.

Note that the minimum/maximum category is used, rather than the category of the minimum/maximum value. The two may be different due to variation in the reference range.

No statistical tests will be performed for this analysis.

10.3.2.3 Assessment of Potentially Clinical Significant Laboratory Variables

The criteria for potentially clinically significant laboratory values will be determined by OMERACT criteria of Grade 3 or 4. For creatine phosphokinase and creatinine, NCI CTC criteria will be used.

The number and percentage of subjects meeting the criteria for potentially clinically significant laboratory values will be summarized by "as treated" treatment group and overall. Only subjects with worsening in grade compared to baseline grade will be captured.

10.3.2.4 Assessment of Liver Elevations

According to FDA's Guidance for Industry "Drug-Induced Liver Injury: Premarketing clinical evaluation" (July 2009), when aminotransferase (AT) abnormalities indicating hepatocellular injury are accompanied by evidence of impaired hepatic function (bilirubin elevation $> 2 \times$ ULN), in the absence of evidence of biliary obstruction (i.e., significant

elevation of ALP) or some other explanation of the injury (e.g., viral hepatitis, alcohol hepatitis), the combined finding (i.e., Hy's Law cases) represents a signal of a potential for the drug to cause severe DILI.

For the purpose of assessing for potential Hy's law cases, the frequencies and percentages of subjects with post baseline liver specific function test values that meet the following criteria of potential clinical interest will be summarized by "as treated" treatment group:

- $ALT \geq 3 \times ULN$
- $ALT \geq 5 \times ULN$
- $ALT \geq 10 \times ULN$
- $ALT \geq 20 \times ULN$
- $AST \geq 3 \times ULN$
- $AST \geq 5 \times ULN$
- $AST \geq 10 \times ULN$
- $AST \geq 20 \times ULN$
- $TBL \geq 2 \times ULN$
- Alkaline phosphatase $\geq 1.5 \times ULN$
- ALT and/or $AST \geq 3 \times ULN$ and concurrent $TBL \geq 1.5 \times ULN$
- ALT and/or $AST \geq 3 \times ULN$ and concurrent $TBL \geq 2 \times ULN$

10.3.3 Analysis of Long Term Laboratory Data

10.3.3.1 Assessment of Mean Change from Baseline in Clinical Laboratory Variables

Analyses of mean change from baseline in continuous hematology, chemistry, and urinalysis variables which are measured longitudinally will be performed by visits and by "as treated" exposure sequences as described in Section 10.1.2. For each change from baseline analysis, the following summary statistics will be presented for each treatment group: sample size, baseline mean, visit mean, and the mean, standard deviation, and median of the changes from baseline.

In addition, similar analyses will be performed for percentage change from baseline in hemoglobin, LDL-C, HDL-C, triglycerides, total cholesterol (TC), TC/HDL and LDL/HDL.

Plot for each exposure sequence over time will be provided for key lab parameters up to Week 48.

Starting with Amendment 5.01.01 (for Japan) and Amendment 6 (for global), subjects receiving upadacitinib 30 mg QD will be switched to upadacitinib 15 mg QD. Mean change from baseline in laboratory values for subjects who switched from upadacitinib 30 mg QD to 15 mg QD will be censored at the time of dose switch, and mean change from baseline for values post switch will be summarized separately, as described in Section 10.1.2.

10.3.3.2 Assessment of Potentially Clinical Significant Laboratory Values

Long-term laboratory data will be summarized based on the number and percentage of subjects meeting the criteria for potentially clinical significant laboratory values and by the actual treatment received at the time of the event occurrence. Starting with Amendment 5.01.01 (for Japan) and Amendment 6 (for global), subjects receiving upadacitinib 30 mg QD will be switched to upadacitinib 15 mg QD. The treatment exposure groups for summarizing potentially clinical significant laboratory values are the same as the ones for long-term AE analysis as described in Section 8.1 and Section 10.1.2.

In the evaluation of potentially clinically significant laboratory values, the baseline value will be determined by the last non-missing measurement recorded on or before the date of the first dose of study drug in the corresponding treatment group (which may be different than the first dose of study drug received in the study). For example, for a subject who started on MTX and switched to Upadacitinib 15 mg QD + MTX combo therapy, lab values under Upadacitinib 15 mg QD exposure would be evaluated against the baseline value defined as the last non-missing measurement recorded on or before the date of the

first dose of Upadacitinib 15 mg QD. For subjects who switched from upadacitinib 30 mg QD to upadacitinib 15 mg QD, lab values under upadacitinib 15 mg QD exposure would still be evaluated against the baseline defined based on the first dose of Upadacitinib 30 mg QD.

A listing of all subjects with any laboratory determination meeting OMERACT criteria of Grade 3 or 4 will be provided by Grade. For creatinine phosphokinase and creatinine, NCI CTC criteria will be used. Only subjects with worsening in grade compared to baseline grade will be captured. For each of these subjects, the whole course of the respective parameter will be listed.

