8.0 Study Drug Exposure and Compliance

8.1 Study Drug Exposure

The duration of exposure to study drug will be summarized for the safety analysis set by the following groups.

1. MTX monotherapy

This includes MTX exposure as monotherapy from subjects starting on MTX monotherapy censored at time of rescue to upadacitinib + MTX.

2. Any Upadacitinib 15 mg QD

This includes Upadacitinib 15 mg QD exposure from subjects starting on Upadacitinib 15 mg QD and subjects rescued from MTX to Upadacitinib 15 mg QD + MTX.

3. Upadacitinib 15 mg QD mono

This includes Upadacitinib 15 mg QD monotherapy exposure from subjects starting on Upadacitinib 15 mg QD monotherapy and censored at time of rescue to upadacitinib 15 mg QD + MTX or with addition of background csDMARD.

4. Any Upadacitinib 30 mg QD

This includes Upadacitinib 30 mg QD exposure from subjects starting on Upadacitinib 30 mg QD and subjects rescued from MTX to Upadacitinib 30 mg QD + MTX. Exposure is censored at time of dose switch from Upadacitinib 30 mg QD to Upadacitinib 15 mg QD.

5. Upadacitinib 30 mg QD mono

This includes Upadacitinib 30 mg QD monotherapy exposure from subjects starting on Upadacitinib 30 mg QD monotherapy and censored at time of rescue to upadacitinib 30 mg QD + MTX or with addition of background csDMARD. In addition, exposure is censored at time of dose switch from Upadacitinib 30 mg QD to Upadacitinib 15 mg QD.

6. Any Upadacitinib 15 mg QD switched from any Upadacitinib 30mg QD

This includes Upadacitinib 15 mg QD exposure from subjects who switched dose from Upadacitinib 30 mg QD to Upadacitinib 15 mg QD.

7. Upadacitinib 15 mg QD mono switched from Upadacitinib 30mg QD mono

This includes Upadacitinib 15 mg QD monotherapy exposure from subjects who started and remained on Upadacitinib 30 mg QD monotherapy (without rescue or addition of background csDMARD) and switched dose from Upadacitinib 30 mg QD to Upadacitinib 15 mg QD. Exposure is censored at time of addition of background csDMARD.

In addition to the groups above, the Japan sub-study has the additional groups of Any Upadacitinib 7.5 mg QD and Upadacitinib 7.5 mg QD monotherapy.

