10.2.2 Analysis of Long Term Adverse Event Rates

Long term adverse event rates will be analyzed using event rates adjusted by cumulative exposure and will be based on the actual treatment received at the time of AE occurrence. Starting with Amendment 5.01.01 (for Japan) and Amendment 6 (for global), subjects receiving upadacitinib 30 mg QD will be switched to upadacitinib 15 mg QD. For these subjects, adverse events and exposure to upadacitinib 30 mg QD will be censored at the time of dose switch; subsequent adverse events and exposure starting the day of first dose

of upadacitinib 15 mg QD will be summarized under separate groups. The detailed treatment exposure groups, including the handling of dose switch, are described in Section 8.1.

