10.3.3.3 Assessment of Liver Elevations

The frequencies and percentages of subjects with post-baseline liver-specific function test values that meet the criteria of potential clinical interest (as described in Section 10.3.2.4) will be summarized by the actual treatment received at the time of the event occurrence. Starting with Amendment 5.01.01 (for Japan) and Amendment 6 (for global), subjects receiving upadacitinib 30 mg QD will be switched to upadacitinib 15 mg QD. The treatment exposure groups for summarizing liver elevations are the same as the ones for long-term AE analysis as described in Section 8.1 and Section 10.1.2.

A subject can be counted under different exposure groups if he/she switched study drug and experienced potentially clinical significant laboratory values under different exposure groups.

A listing of potentially clinically significant liver elevations based on criteria specified above will be provided. For each of these subjects, the whole course of the respective parameter will be listed.

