10.4.3 Analysis of Long Term Vital Sign

Analyses of mean change from baseline in continuous vital signs variables which are measured longitudinally will be performed by visits and by "as treated" exposure

sequences as described in Section 10.1.2. For each change from baseline analysis, the following summary statistics will be presented for each treatment group: sample size, baseline mean, visit mean, and the mean, standard deviation, and median of the changes from baseline.

Long Term Vital Sign will also be summarized based on the number and percentage of subjects meeting the criteria for potentially clinical significant vital sign values and by the actual treatment received at the time of the event occurrence. The treatment exposure groups are the same as the ones for long-term AE analysis as described in Section 8.1.

In the evaluation of potentially clinically significant vital sign values, the baseline value will be determined by the last non-missing measurement recorded on or before the date of the first dose of study drug in the corresponding treatment group, similarly as described in Section 10.3.3.2.

Starting with Amendment 5.01.01 (for Japan) and Amendment 6 (for global), subjects receiving upadacitinib 30 mg QD will be switched to upadacitinib 15 mg QD. Mean change from baseline in vital signs for subjects who switched from upadacitinib 30 mg QD to 15 mg QD will be censored at the time of dose switch, and mean change from baseline for values post switch will be summarized separately, as described in Section 10.1.2. The treatment exposure groups for summarizing potentially clinical significant vital sign values are the same as the ones for long-term AE analysis as described in Section 10.2.2 and Section 10.1.2. For the purpose of evaluating potentially clinical significant vital sign values, for subjects who switched from upadacitinib 30 mg QD to upadacitinib 15 mg QD, baseline is defined based on the first dose of Upadacitinib 30 mg QD, similarly as described in Section 10.3.3.2.

A listing of all subjects with any vital sign values meeting the criteria for potentially clinically significant vital signs will be provided. For each of these subjects, the whole course of the respective parameter will be listed.

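### Long-term laboratory, liver and vital-sign abnormalities are given only as crude percentages in exposure groups of unequal length, which can mislead on 15 mg versus 30 mg if risk continues over time

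*SAP*

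**What the plan says.** Three long-term outputs report the share of subjects who ever meet an abnormality criterion, by treatment received at the time of the event:

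- Laboratory values (SAP 10.3.3.2): "Long-term laboratory data will be summarized based on the number and percentage of subjects meeting the criteria for potentially clinical significant laboratory values".
- Liver elevations (SAP 10.3.3.3): "The frequencies and percentages of subjects with post-baseline liver-specific function test values that meet the criteria of potential clinical interest".
- Vital signs (SAP 10.4.3): "summarized based on the number and percentage of subjects meeting the criteria for potentially clinical significant vital sign values".

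The grouping is shared with the safety event tables: "The treatment exposure groups for summarizing potentially clinical significant laboratory values are the same as the ones for long-term AE analysis". SAP 10.3.3.3 and 10.4.3 say the same for liver and vital-sign values, and 10.1.2 confirms it for laboratory and vital-sign values.

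Those groups are defined in SAP 8.1 and end or begin at different points. For MTX: "This includes MTX exposure as monotherapy from subjects starting on MTX monotherapy censored at time of rescue to upadacitinib + MTX". For 30 mg: "Exposure is censored at time of dose switch from Upadacitinib 30 mg QD to Upadacitinib 15 mg QD". The upadacitinib monotherapy groups also stop when MTX or a background csDMARD is added. The groups switched from 30 mg to 15 mg begin only at the switch. The group for any 15 mg exposure is not cut at that point.

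For adverse events in the same groups, SAP 10.2.2 uses a different measure: "Long term adverse event rates will be analyzed using event rates adjusted by cumulative exposure". No section gives a person-time rate, a time-to-first-event estimate or a common time cut for the three abnormality outputs.

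**The concern.** The chance that a subject has ever shown an abnormal value cannot fall as follow-up lengthens, and it rises wherever risk continues. A crude percentage therefore mixes risk with length of observation. When one group can run for 260 weeks and another is closed at a mid-study dose switch, their percentages are not on the same footing.

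What is at stake is how the long-term dose comparison is read. The 30 mg group is the one cut short, so a dose-related laboratory or blood-pressure signal could be diluted. The post-switch 15 mg group could look reassuring partly because it was watched for less time.

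**Working it through.** The plan states no figure for these summaries, so there is none to reproduce. The check bounds the group lengths from the documents' dates and then asks what those lengths do to a percentage.

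**1. Group lengths.** Inputs: treatment up to 260 weeks (Protocol synopsis); original protocol 1 October 2015, Japan Amendment 5.01.01 15 July 2019 and Amendment 6 16 December 2019 (Protocol 1.1); all subjects at the end of Period 1 as of September 2018 (Protocol 5.5.5.2); switch starting with those two amendments (SAP 7.0).

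- Maximum exposure: 260 × 7 / 365.25 = 4.98 years.
- Latest randomization: 30 September 2018 minus 48 × 7 days = 29 October 2017.
- 30 mg up to the Amendment 6 date: 2.13 years (from 29 October 2017) to 4.21 years (from 1 October 2015).
- Post-switch 15 mg: 4.98 − 4.21 = 0.8 years to 4.98 − 2.13 = 2.9 years.
- Japan, switch at 15 July 2019: 30 mg about 1.7 to 3.8 years; post-switch about 1.2 to 3.3 years.
- MTX: 26 × 7 / 365.25 = 0.5 years if rescued at Week 26; up to 4.98 years if not.

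These are bounds for subjects who stay on treatment. Switching later than the amendment date would lengthen 30 mg and shorten post-switch exposure. Mean exposure per group is not in the documents.

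**2. Percentages under equal risk.** Assumption, not in the documents: the same constant rate in every group. Ever-abnormal percentage = 100 × (1 − exp(−rate × years)).

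| Rate per 100 PY | 1.5 y | 3 y | 5 y | 5 y / 3 y | 5 y / 1.5 y |
|---|---|---|---|---|---|
| 2 | 3.0% | 5.8% | 9.5% | 1.63 | 3.22 |
| 5 | 7.2% | 13.9% | 22.1% | 1.59 | 3.06 |
| 10 | 13.9% | 25.9% | 39.3% | 1.52 | 2.82 |

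The ratios hardly depend on the rate. Here 5 years is the ceiling for 15 mg, 3 years lies inside the 30 mg range, and 1.5 years lies inside the post-switch range.

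**3. Masking.** With 5 years on 15 mg and 3 years on 30 mg, a rate 5/3 as high on 30 mg gives the same percentage. For example, 0.03 × 5 = 0.05 × 3 = 0.15, and 1 − exp(−0.15) = 13.9% in both groups, although the rate on 30 mg is 67% higher.

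**4. Early risk only.** Suppose the rate is 10 per 100 PY in the first half-year and zero afterwards. Groups that begin at first dose then show 1 − exp(−0.05) = 4.9% at 0.5, 1.5, 3 and 5 years alike. The divergence in step 2 therefore needs continuing risk.

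**5. Visit density.** Post-baseline visits: 13 in the 48 weeks of Period 1 and 17 in the 212 weeks of Period 2 (Protocol 5.1). Per year: 13 / (48 × 7 / 365.25) = 14.1 against 17 / (212 × 7 / 365.25) = 4.2. Post-switch time lies wholly in Period 2, so transient abnormalities are looked for less often there.

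**The case against.** The best reply is that these tables are descriptive and do not stand alone. No test or between-group difference is planned for the percentages. SAP 8.1 tabulates exposure for the same groups. Mean changes are shown by visit, with post-switch values separate, and full-course listings are planned. Hepatic disorder, anemia, neutropenia, lymphopenia, CPK elevation and renal dysfunction are given per 100 patient-years as adverse events of special interest. The tables before Week 26 share a common window and are unaffected. All of this stands and limits the harm, but none of it adjusts the percentages. Protocol 6.1.1.1 restricts which laboratory and vital-sign changes count as adverse events, and blood pressure and weight have no special-interest counterpart.

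A second reply is that patient-year rates are not a full cure. That also stands. Unequal visit density can give unequal rates at equal risk. If risk is early only, rates fall as quiet time accumulates, which is a reason to keep the percentage as well.

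Three stronger readings are tempting, and the documents do not support them:

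- A reader might infer that MTX will look safest because it is cut at rescue. Only MTX subjects who at Week 26 miss both CDAI remission and the joint-count improvement leave the group. The rest can continue to Week 260, and MTX time is not cut when a csDMARD is added, unlike upadacitinib monotherapy. The direction depends on rescue and dropout figures that are not given.
- A reader might infer that equal-risk groups must look different. Step 4 shows otherwise.
- A reader might infer that the SAP adjusts adverse events because it recognizes the unequal lengths. SAP 10.2.2 gives no reason.

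**Conclusion.** The point holds as a problem of interpretation in the long-term descriptive tables. The firm contrast is 15 mg from baseline against 30 mg and post-switch 15 mg, because the dose switch closes one group and opens another while leaving the first uncut. For MTX no direction can be fixed.

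The size is conditional. With an equal, constant rate between 2 and 10 per 100 patient-years, length alone can multiply a percentage by about 1.5 to 1.6 (5 against 3 years) or 2.8 to 3.2 (5 against 1.5 years). The rate is an assumption. The 5 years is an individual maximum before dropout, so actual group averages may differ by less. Persisting abnormalities could also partly offset the shorter post-switch time, since SAP 10.3.3.2 keeps the 30 mg baseline after the switch. Neither the Period 1 results nor type I error is affected.

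**What to change.** In SAP 10.3.3.2, 10.3.3.3 and 10.4.3:

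- Beside each percentage, add the number of subjects with a first event per 100 patient-years, with 95% CI. Person-time ends at the first event or at the end of that exposure group, using the SAP 8.1 definitions. Keep the percentage.
- State how subjects already abnormal at the dose switch are handled in the post-switch groups: whether a persisting abnormality counts as a new event, and whether such subjects contribute person-time.
- Add a note that the sparser Period 2 visit schedule limits comparison of post-switch groups with groups that include Period 1.

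The cost is some programming, since first-event person-time is needed for each criterion and exposure group, and extra table columns. No new data are needed. SAP 11.1 says the current version applies only to long-term reporting still to come, so completed Period 1 results are untouched.
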